25.2.3.4 Maternal mortality (any cause)

25.2.3.4.1 Derivation

This outcome is present where the event details form indicates that the participant has died and gives a date of death.

25.2.3.4.2 Analysis

This outcome will be analysed using the methods described in section 25.2.2.

25.2.3.5 Maternal severe acute respiratory infections

25.2.3.5.1 Derivation

This outcome is present where the event details form indicates that any cause of death or near miss is infection related, and the suspected type of infection is selected as either "Respiratory infection" or "COVID-19"

25.2.3.5.2 Analysis

This outcome will be analysed using the methods described in section 25.2.2.

25.2.3.6 Quantitative implementation outcomes

25.2.3.6.1 **Derivation**

Quantitative implementation outcomes are measured in all APT-Sepsis and control facilities.

- compliance with hand hygiene (as per WHO 5 movements of hand hygiene standard assessment)
 - o proportion of observed hand hygiene opportunities which were taken
- correct use of antibiotic prophylaxis for prevention of peripartum infection (as per WHO guidelines),
 - o proportion of caesarean sections given antibiotic prophylaxis
- complete vital sign recording at admission
 - o proportion of in-patients with complete vital signs recorded at admission
- Sepsis management compliance:
 - o proportion of infection cases with complete vital signs recorded
 - o proportion of infection cases given fluids within 1 hour
 - o proportion of infection cases given antibiotics within 1 hour

25.2.3.6.2 Analysis

All implementation outcomes are only measured in the post-intervention period, with each site receiving three visits to assess these outcomes. Analysis will focus on the cluster level, with cluster-level outcomes being calculated as proportions at each of the three visits. Analysis will use mixed-effect

repeated-measures linear regression models to compare APT-Sepsis and Control sites. Country, and the minimisation factor facility size will be included as covariates.

26 Safety Evaluations

The primary and secondary outcomes are all related to safety, and other outcomes. Other safety outcomes, that may potentially be influenced by the intervention, such as caesarean section rates, are presented descriptively as described above in the Facility and Patient characteristics section.

27 Additional Analyses

There are no planned additional analyses. We are not collecting information on individual women who did not experience a severe infection, near-miss or maternal mortality therefore a fully covariate adjusted analysis will not be possible.

28 Document History

Statistical Analysis Plan Version	Protocol Version	Section number(s) changed	Description of changes	Justification for changes	Date Implemented
2.0	Malawi: version 6.0 07/11/2024 Uganda: version 3.0 07/11/2024	25.2.3.4.1	Changed the derivation of the outcome to use the patient database rather than the facility database	The derivation was incorrect, the maternal mortality outcome should be based on deaths recorded in the patient database, rather than summary numbers in the facility database.	04/08/2025

29 References

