6.3.2 Secondary Objective(s)

Secondary Objectives Secondary Outcome Measures Timepoint(s) of evaluation				
To evaluate if the APT-Sepsis programme is effective at reducing secondary clinical outcomes of: Stillbirth, early neonatal death (infection - related and total), maternal mortality (any cause), maternal near miss (any cause)	 Stillbirth, Early neonatal death (infection - related and total), Maternal mortality (any cause), Maternal near miss (any cause). Maternal severe acute respiratory infections Compliance with APT-Sepsis implementation 	Timepoint(s) of evaluation Daily observation of the routine health facility records. From the baseline phase to the end of cluster participation. Outcomes will be collected from all women who are admitted to the healthcare facility during pregnancy or within 42 days of delivery. Follow-up of events will occur for up to 28 days until death or discharge from a healthcare facility, whichever is sooner.		
To explore differential or subgroup effects of the APT-Sepsis programme.	Sub-groups that have been specified are: a) country b) facility size (number of births) c) high vs. low performing facilities (defined by quantitative implementation fidelity assessment)			
Implementation: To understand the implementation of the APT-Sepsis programme in Malawi and Uganda, to facilitate interpretation of trial outcomes and development of a longer-term implementation strategy.	Implementation outcomes: Fidelity, Sustainability Acceptability, Understand the mediators of implementation including the impact of context	From the implementation of the intervention to the end of cluster participation.		

Secondary Objectives	Secondary Outcome Measures	Timepoint(s) of evaluation
Health economic analysis: To determine if the APT-Sepsis programme is cost effective.	The health economic analysis will be based on the principal outcome of the trial and be reported in terms of disaggregated costs and consequences and cost per major outcome averted where major outcome is defined as maternal infection-related mortality and severe morbidity.	The data collection will be conducted during the period of study implementation. The economics analysis will take place in the last 13 months of the study.

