11.3 Removal of participants from intervention or follow-up

At present there are no planned instances where a participant or facility would be removed from the intervention or post intervention roll out period. Facilities that drop out during the baseline period will not be included in the final analysis.

12 Method of assignment to intervention

A minimisation system was configured by an independent statistician at LCTC. Health facilities were allocated to treatment arms using a minimisation algorithm, to ensure balance of important factors between facilities allocated to the intervention and control groups. The minimisation factors within each country were

- 1. number of births per cluster per week: three categories: cut points 70.8 and 118.5 (Malawi), 60.5 and 83.9 (Uganda).
- 2. proportion of births with the composite primary outcome (infection related maternal mortality, infection related maternal near-miss and severe infection related morbidity see Section 15.1): two categories: cut points 1.96 (Malawi), 3.19 (Uganda).

These were be measured at each facility within the baseline period. The cut points for the minimisation factors were determined separately for each country. Weekly average births were assigned into 3 categories using the 33rd and 67th percentile of the observed values within up to the first four months of the baseline periods. Start dates were staggered, therefore, we had between two and four months of baseline data for each facility to determine cut-points. Proportion of births with the composite primary outcome were assigned into 2 categories using the median as a cut-off point. Facilities were allocated during the fifth month of their baseline period, using their baseline data up to this point (at least four months for each facility).

The minimisation algorithm will calculate the allocation which will minimise imbalance over all minimisation factors. A random element of 90% will be incorporated to reduce predictability of allocation, with facilities allocated to the group which minimises imbalance with probability 0.9, or to the other group with probability 0.1. If both allocations would result in equal imbalance, the allocation will be determined completely at random [1].

13 Schedule of assessments

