25.2.2.2 Analysis

Summary statistics of the number and percentage who experienced the outcome will be presented by trial arm, country and time-period. The denominator for the percentage calculation will be the number of live births recorded in the facility in the time period.

Outcome rates over time will be presented in a line graph, split by intervention vs control, with prerandomisation, transition and post-randomisation phases marked. Time will be anchored around date of allocation to the transition phase for each facility.

The primary analysis will use a mixed effects logistic regression models with robust standard errors. A small sample correction will not be used as there are over 40 clusters [8] The model will incorporate a constrained baseline analysis [9], where both pre-randomisation and post-randomisation time points are included as outcomes, but with the treatment effect assumed to be zero in the pre-randomisation phase. This will be implemented using two binary covariates, one indicating period (0= pre-randomisation, 1=post-randomisation), and one indicating exposure to the intervention (taking the value 0 for all clusters in the pre-randomisation period, and control clusters in the post-randomisation period, and the value 1 for the intervention clusters in the post-randomisation period). Facility and facility by period will be included as random effects, with country, and the categorical minimisation factor facility size included as covariates. The second minimisation factor (proportion of births with the composite primary outcome) is not included as proportion of births is already in the model as the outcome variable. Relative risk and risk differences will be derived using marginal standardisation, as in Kirkwood et al [10]. Under this approach, the mean risk under the control condition and intervention condition is obtained. The risk ratio is then derived using the mean risk in intervention condition and by the mean risk in the control condition, with the calculation being performed on the log scale. The risk difference is derived as the mean risk in intervention condition minus the mean risk in the control condition. We will use the unconditional standard errors to obtain the confidence interval, as this allows for correlation amongst the observations. Point estimates, 95% confidence intervals and exact p-Values will be reported. Estimation of the relative risks and risk differences, and their standard errors and confidence intervals

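### The implementation-outcome models leave out the baseline-rate minimisation factor without giving a reason, and the protocol timetable dates the compliance measure from baseline

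*SAP*

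**What the plan says.** **Allocation.** SAP section 12 minimises within country on two factors: weekly births in three bands, and the "proportion of births with the composite primary outcome" in two. On the second it says: "Proportion of births with the composite primary outcome were assigned into 2 categories using the median as a cut-off point". The cut points are 1.96 in Malawi and 3.19 in Uganda.

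**Implementation outcomes.** These cover hand hygiene, antibiotic prophylaxis at caesarean section, vital signs at admission and sepsis management. SAP 25.2.3.6.1 says: "Quantitative implementation outcomes are measured in all APT-Sepsis and control facilities". On timing, SAP 25.2.3.6.2 says: "All implementation outcomes are only measured in the post-intervention period". Each facility is visited three times. The model is a linear repeated-measures mixed model on facility proportions at each visit. On adjustment: "Country, and the minimisation factor facility size will be included as covariates". The second minimisation factor is not mentioned.

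**Primary outcome.** SAP 25.2.2.2 also leaves that factor out, but explains why: it "is not included as proportion of births is already in the model as the outcome variable".

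**Protocol timetable.** The table in Protocol 6.3.2 places compliance with the programme in the same row as the clinical secondary outcomes. That row describes daily review of routine records, with the timepoint "From the baseline phase to the end of cluster participation". A separate row for fidelity, sustainability and acceptability starts when the intervention is implemented.

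**The concern.** When allocation is balanced on a factor, the variance of the treatment contrast no longer contains that factor's contribution. A model that omits the factor still leaves its contribution in the residual, so the standard error is overstated to the extent that the factor predicts the outcome. The SAP follows this logic for country and facility size, and for the primary model it explains the one exception. For the implementation outcomes it neither adjusts nor explains.

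These outcomes are to be reported beside the clinical comparison (Protocol section 19) and bear on whether the programme changed care. They have no baseline compliance measurement to draw precision from, so the design factors are worth using in full. The timetable entry adds a smaller problem: protocol and SAP disagree on when, and from what source, compliance is measured.

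**Working it through.** **1. Does the stated reason carry over?** No plan figure bears on this, so the two models are compared.

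| | Primary model (25.2.2.2) | Implementation models (25.2.3.6.2) |
|---|---|---|
| Outcome | composite event | compliance proportion |
| Baseline data in the model | yes, as outcome | none |
| Country and size adjusted | yes | yes |
| Baseline-rate category adjusted | no, reason given | no, no reason given |

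The reason depends on the first two rows. Baseline composite events inform the facility effects in the primary model. In the implementation models no composite data of any period appear, so the reason does not apply.

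**2. What does the omission cost?** The inputs from the documents are 60 facilities, 30 per country (Protocol section 7); three size bands, two rate bands and minimisation probability 0.9 (SAP section 12); and 95% intervals (SAP 25.2.1). The share R² of the variance of the facility mean that the rate category explains is in neither document. It is assumed, over 0 to 0.30.

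If the factor is balanced between arms, the approximate ratio of standard errors, omitted to included, is 1/√(1 − R²):

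- R² = 0.05: 1/√0.95 = 1.026
- R² = 0.10: 1/√0.90 = 1.054
- R² = 0.20: 1/√0.80 = 1.118
- R² = 0.30: 1/√0.70 = 1.195

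A simulation of 4,000 minimised allocations, with a linear model on the facility mean containing arm, country and size, gave the following. Coverage is 100% minus the simulated null rejection rate.

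| Assumed R² | SE ratio, omitted/included | Coverage of 95% interval, omitted | Coverage, included |
|---|---|---|---|
| 0 | 0.999 | 94.8% | 94.7% |
| 0.05 | 1.027 | 95.7% | 95.4% |
| 0.10 | 1.056 | 96.2% | 95.0% |
| 0.20 | 1.122 | 97.1% | 94.8% |
| 0.30 | 1.205 | 97.5% | 94.7% |

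A separate run of 3,000 trials gave included/omitted ratios of 0.975, 0.946, 0.891 and 0.831 for R² of 0.05 to 0.30. Their inverses are 1.026, 1.057, 1.122 and 1.203, in agreement. The error is always in the conservative direction.

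**3. What does inclusion cost?** Without the factor the facility-level model has five parameters (intercept, arm, country, two for size), leaving 60 − 5 = 55 degrees of freedom. With it, 54 remain. At R² = 0 the standard error changes by about 0.1%.

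**4. Timing.** SAP section 24 says the quantitative implementation outcomes are collected to assess compliance with the programme, so they are the measure named in the first row of the Protocol 6.3.2 table. That row says routine records from the baseline phase. The SAP says visits by the study team after the intervention. The two cannot both describe the measure.

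**The case against.** **The size is an assumption.** This stands. Nothing in the documents links baseline infection rate to compliance, and a median split may explain little. The model uses visit-level proportions, so visit noise dilutes any share defined on between-facility variance alone. For example, if visit variance equals between-facility variance, a three-visit mean has variance 1 + 1/3, and 30% becomes 0.30/(4/3) = 22.5%, while 10% becomes 7.5% (SE about 4% larger, since 1/√0.925 = 1.040). The upper end of the range should not be read as an expectation.

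**The outcomes are exploratory.** This also stands. Protocol 17.4 and SAP 25.2.3 present secondary outcomes with intervals and no testing, so only interval width is affected.

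**The timetable conflict is narrow.** Largely right. One timepoint serves several measures in that row, and observed hand-hygiene opportunities cannot come from routine records. The separate implementation row agrees with the SAP.

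**Stronger readings a reader might infer, which the documents do not support:**

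- That the SAP drops the factor here for the primary model's reason. Section 25.2.3.6.2 gives no reason.
- That the comparison is biased or exposed to uncorrected imbalance. Minimisation with probability 0.9 limits imbalance on this factor, and the simulated intervals over-cover.
- That the factor is the only baseline measure of quality of care. It is an outcome rate, and SAP section 23 lists weekly facility measures at baseline (soap, water, thermometers, antibiotics) closer to the care processes.
- That the protocol promises change from baseline in compliance. No section does, and 25.2.3.6.2 already describes a comparison of the two arms.

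**Conclusion.** The point holds as one of lost precision and incomplete specification. A factor used to allocate facilities is missing from the implementation models, no reason is given, and the only reason elsewhere in the SAP does not fit. The cost is a standard error about 3% to 20% too large if the factor explains 5% to 30% of the variance of the facility mean, and nothing if it explains none. These figures rest on that assumed range, on 60 facilities, and on a facility-mean model standing in for the repeated-measures model. The validity of the between-arm comparison is not in question. The change is worth making because inclusion costs almost nothing whatever the true share. The timetable mismatch is a real but small inconsistency, confined to the compliance entry.

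**What to change.** 1. In SAP 25.2.3.6.2, add the binary baseline-rate category, with the country-specific cut points 1.96 (Malawi) and 3.19 (Uganda), as a covariate beside country and facility size. The value was needed for allocation, so it is already held for every randomised facility. The cost is about one degree of freedom of 55, with no new data. The amendment should be dated before these outcomes are compared by arm.
2. In Protocol 6.3.2, give the compliance measure its own timepoint: the three post-intervention visits, in both arms. The Malawi protocol was not among the documents reviewed, and its matching entry should be checked.
3. While editing, reconcile the general statement in SAP 25.2.3, that all secondary outcomes are binary and follow the primary methods, with the linear repeated-measures model in 25.2.3.6.2. One sentence of exception is enough.

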15 END OF STUDY

The end of the trial is defined to be the date on which data for all participants is frozen and data entry privileges are withdrawn from the trial database. The trial may be closed prematurely by the Trial Steering Committee (TSC), on the recommendation of the Independent Data Monitoring Committee (IDMC).

Facility closure activities will be centrally coordinated and conducted in accordance with LCTC processes regardless of whether the trial closes as planned or prematurely. This includes activities such as:

- End of Trial notification to REC
- Study-related materials reconciled and returned/disposed of as appropriate.
- All facility data entered onto the study database, discrepancies raised and satisfactory responses received.
- Quality Control checks of the Investigator Site Files and Trial Master File as appropriate.

16 **SAFETY REPORTING**

This trial seeks to implement recognised best practice at a health care setting level. The intervention seeks to improve compliance with WHO guidance and evidence based best practice around infection prevention and management, and therefore improve quality of care and health outcomes.

There are no novel treatments or medications being recommended in this study.

The basis of the intervention is to improve compliance with recognised best practice. These practices are already in use throughout the world, although they are unfortunately not consistently and reliably applied in all settings. Therefore, we do not anticipate adverse events as a direct consequence of the trial.

We recognise that in these settings there will be a range of important adverse outcomes as a consequence of infection and sepsis. Infection-related adverse and non-infection specific outcomes (including death, near miss, severe morbidity and stillbirth and neonatal deaths) data will be measured throughout the study at every facility. Other outcomes, that may potentially be influenced by the intervention, such as caesarean section rates, will also be presented in the IDMC safety report. These outcomes will be monitored by the IDMC and reported by trial arm (the intervention is not blinded). The report content will be detailed in the IDMC charter.

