Expedited reporting of individual events is not likely to provide any safety benefit as intervention effects are likely to be small compared to the background rate of such events and adjustment for clustering will be required to interpret if differences in death rates are due to the intervention.

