22.2 Safety Analyses

Facilities randomised to APT-Sepsis who do not begin the APT-Sepsis programme will be included in the control safety group. Facilities randomised to control who begin the APT-Sepsis programme will be included in the APT-Sepsis safety group.

23 Facility and patient Characteristics

Characteristics of both the facilities and the included participants will be presented, split by treatment allocation and by time-period (baseline or post intervention roll out). Categorical data will be presented using counts and percentages, continuous data will be presented using mean, standard deviation, median, interquartile range, minimum and maximum. There will be no statistical testing of baseline characteristics.

For characteristics collected weekly, the weekly average at site will be computed and then the average of all sites will be presented. For characteristics collected as available, limited or none, the average proportion of time that they had full availability, limited availability or no availability will be presented.

The following characteristics collected weekly will be presented summarised by facility

- Labour ward theatres in operation
- Functioning autoclaves within the facility
- Equipment available
 - o X-ray
 - Ultrasound facilities
 - FBC testing

LCTC_ST003_TEMP1: SAP Template, V0.1, 08/01/2021

(developed using LCTC_GE001_TEMP4: LCTC Template of a Template, V1.0, 04/09/2020)

- Renal function testing
- Blood culture testing
- Wound swab testing
- Urine microscopy
- Pregnancy tests
- Beds available
- · Beds occupied
- Nurses/midwives working
- Equipment for IV-line insertion
- Working thermometers
- Working BP devices
- Working pulse oximetry machines
- Availability of:
 - Fetoscopes/pinards/fetal stethoscopes
 - o Clocks/watches
 - Spare batteries
 - Urine dipsticks
 - Malaria rapid tests
 - Working O2 concentrators
 - o Bottled or piped O2
 - o Gloves
 - o Soap
 - o Running/flowing water for handwashing
 - Hand drying facilities
 - Alcohol rub for hand cleaning
- Availability of Oral Antibiotics
 - Azithromycin
 - o Amoxicillin
 - o Augmentin
 - Cephalosporin
 - Ciprofloxacin
 - Clindamycin
 - Co-amoxiclav
 - Doxycycline
 - Erythromycin
 - o Flucloxacillin
 - Metronidazole
- Availability of IV antibiotics:
 - o Ampicillin
 - Benzylpenicillin
 - Cefazolin

LCTC_ST003_TEMP1: SAP Template, V0.1, 08/01/2021

(developed using LCTC_GE001_TEMP4: LCTC Template of a Template, V1.0, 04/09/2020)

- Cephalosporin
- Chloramphenicol

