- Ciprofloxacin
- Clindamycin
- Co-amoxiclav
- Gentamycin
- Metronidazole
- o Penicillin G
- Vancomycin
- o Meropenem
- o Tazobactam (Tazocin) or Piperacillin/Tazobactam
- Availability of other supplies
 - o IV fluids (0.9% Saline or Hartmann's or Ringers lactate)
- Availability of labour ward equipment (additional)
 - o Antiseptics for skin preparation
 - Surgical gloves
 - o Sterile (clean) linen packs
 - o Disposable delivery kit ("Mamta kit")
 - Sufficient sterilized delivery sets
 - Sterilized gowns
 - Sterilized forceps set
 - Working vacuum extractor
 - Suction apparatus with suction tube
 - Laceration repair pack
 - o Emergency drugs (with expiration limits)
 - o Mucus extractor for neonates
 - o Bag valve mask (ambu bag) for newborn

The following 'participant' characteristics will be presented based on numbers reported at each site:

- Total number of births (total, caesarean and vaginal)
- Total number of early pregnancy losses
- Proportion of cases of PPH blood loss more than 1 litre
- Proportion of those with pre-eclampsia/eclampsia
- Proportion of instrumental deliveries (forceps, vacuum, ventouse)
- Proportion of neonatal deaths (inpatients)

The following participant characteristics will be presented for all women who are included in the trial data set due to severe infection, near miss or death, and also for those who were judged to have had severe infection, infection related near miss or infection related death.

• Age

- Pregnancy/post-delivery status on admission
- Surgical procedure during current pregnancy/post-delivery period

24 Compliance with Intervention

Key quantitative implementation outcomes will be collected in order to assess APT-Sepsis programme compliance. These are calculated from observations taken at quarterly visits to facilities by the study team. Summaries of these will be presented by facility for those randomised to the intervention.

- compliance with hand hygiene (as per WHO 5 movements of hand hygiene standard assessment)
 - o proportion of observed hand hygiene opportunities which were taken
- correct use of antibiotic prophylaxis for prevention of peripartum infection (as per WHO guidelines),
 - o proportion of caesarean sections given antibiotic prophylaxis
- complete vital sign recording at admission
 - o proportion of in-patients with complete vital signs recorded at admission
- sepsis management compliance:
 - o proportion of infection cases with complete vital signs recorded at diagnosis

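### SAP 26 names the caesarean rate as a safety outcome the programme may influence, but plans no effect estimate or confidence interval that allows for facility clustering

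*SAP*

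**What the plan says.** SAP section 26 treats the caesarean rate as a safety outcome that the programme might change and gives it descriptive presentation only: "Other safety outcomes, that may potentially be influenced by the intervention, such as caesarean section rates, are presented descriptively". The section it points back to is SAP section 23, which lists "Total number of births (total, caesarean and vaginal" births among the participant characteristics. Characteristics there are shown "split by treatment allocation and by time-period (baseline or post intervention roll out" periods, as counts and percentages if categorical and as means, SDs and quantiles if continuous. SAP section 27 closes the other route: "There are no planned additional analyses".

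Protocol section 16 sends the same measure to the monitoring committee: "Other outcomes, that may potentially be influenced by the intervention, such as caesarean section rates, will also be presented in the IDMC safety report". That report is by arm, and its content is left to the committee's charter. Of deaths, the same section says that "adjustment for clustering will be required to interpret if differences in death rates are due to the intervention".

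Two other rules are relevant. Protocol section 17.4 promises point estimates and 95% intervals for all outcomes. SAP section 25.2.3 gives secondary outcomes a modelled effect and interval without a significance test.

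**The concern.** Whole facilities are randomised, and caesarean rates can be expected to differ between facilities for reasons unrelated to the programme. An arm-by-period table shows four rates and invites the reader to compare them. It does not show how far the comparison could move by chance when there are about 30 facilities per arm. The birth counts are large, so a reader who thinks in births will take a small difference to be precise.

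The rate matters beyond safety. The primary composite includes deep surgical site infection, which requires an operation or a birth injury. If caesarean use shifted between arms, a reader of the primary result would want to know by how much and with what uncertainty.

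**Working it through.** **The plan's own figure.** The documents state no caesarean rate, ICC or precision, so there is none to reproduce. The design total does reproduce: 1,500 × 23/12 × 60 = 172,500.

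**Inputs**
- Facilities: 30 per arm (60 facilities, 1:1, Protocol section 7).
- Cluster autocorrelation (CAC): 0.90 to 0.97. This is an assumption, borrowed from the values in SAP section 16.2 for the primary outcome (base 0.97, lower bound 0.9).
- Births: 80 per facility per week. This is an assumption; it lies in the middle size band of both countries in SAP section 12 (70.8 to 118.5 and 60.5 to 83.9). Over 26 baseline weeks, m0 = 2,080. Over 39 post-period weeks, m1 = 3,120.
- Caesarean rate p = 25% and between-facility SD 6 to 10 points. Both are assumptions. ICC = SD²/[p(1−p)], so 0.0036/0.1875 = 0.0192 and 0.01/0.1875 = 0.0533.

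**Formulas** (two periods, normal approximation)
- A = p(1−p) × 2/30 = 0.1875 × 2/30 = 0.0125
- v0 = ICC + (1−ICC)/m0; v1 = ICC + (1−ICC)/m1; c = ICC × CAC
- Constrained-baseline model: V = A × v1 × [1 − c²/(v0 × v1)]
- Difference between arms in change from baseline: V = A × (v0 + v1 − 2c)
- Post-period difference, births treated as independent: V = A/m1
- 95% half-width = 1.96 × √V

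**Widest case** (ICC 0.0533, CAC 0.90). v0 = 0.05379, v1 = 0.05364, c = 0.04800. Model: V = 0.0125 × 0.05364 × (1 − 0.002304/0.002885) = 0.000135, half-width 2.28 points. Change from baseline: V = 0.0125 × (0.05379 + 0.05364 − 0.09600) = 0.000143, half-width 2.34 points.

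**Narrowest case** (ICC 0.0192, CAC 0.97). v0 = 0.01967, v1 = 0.01951, c = 0.01862. The same steps give 0.95 points (model) and 0.96 points (change from baseline).

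**Births treated as independent.** Post-period difference: 1.96 × √(0.0125/3,120) = 0.39 points. Like for like, the change-from-baseline contrast gives 1.96 × √[0.0125 × (1/2,080 + 1/3,120)] = 0.62 points.

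| 95% half-width, points | Assumed inputs above | Second set: rate 20%, ICC 0.021 to 0.05, 750 and 1,125 births |
|---|---|---|
| Constrained-baseline model | 0.95 to 2.28 | 1.2 to 2.2 |
| Change from baseline, with clustering | 0.96 to 2.34 | 1.2 to 2.2 |
| Post-period only, births independent | 0.39 | 0.6 |

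The second set takes 1,500 births a year (750 in 6 months, 1,125 in 9) and an ICC range starting at the 0.021 estimated for the primary outcome at baseline. Its rate and ICC are still assumptions for caesareans. Over a wider range (rate 10 to 30%, ICC 0.01 to 0.10), the model half-width runs from about 0.8 to 3.3 points.

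**Can the model be fitted?** It needs only caesareans and total births by facility and period, and SAP section 23 already tabulates these from site reports. Stillbirth is the precedent: SAP section 25.2.3.2 takes it from daily facility counts and analyses it by the primary method with its own denominator.

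**The case against.** The strongest reply is that the table already holds most of the information. Because it is split by period as well as arm, the change-from-baseline contrast can be worked out, and it is almost as precise as the model: 0.96 to 2.34 points against 0.95 to 2.28. That stands. A reader might infer a large gain by setting a post-period-only comparison against the model. With the same inputs, the chance that the interval excludes zero for a true 2-point rise is 12 to 25% post-period only and 41 to 98% with the model. That is not the gain from the fix, because the planned table does not confine anyone to the post-period; the change-from-baseline contrast gives 39 to 98%. What is missing is the stated interval.

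Second, the caesarean rate is not in the outcome list of SAP section 15.2, none of the three intervention domains targets mode of birth, and descriptive reporting of extra safety measures is common. A reader might infer that Protocol section 17.4 or the clustering remark in Protocol section 16 is breached. The documents do not clearly support that: the first speaks of outcomes generally and the second of death rates. Still, SAP section 26 itself calls the rate a safety outcome, and the reason for allowing for clustering is the same.

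Third, SAP section 23 could be read as giving site-level means and SDs, which would show some between-facility spread. It would still give no interval for the effect. The monitoring committee sees the rate by arm, but its charter is not among the documents and its report does not replace the final analysis. SAP section 6 also allows unplanned analyses with justification, so it would be too strong to say that the trial could never answer the question.

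**Conclusion.** The gap is real and limited: a named safety outcome has no planned effect estimate and no interval that allows for clustering. Its true uncertainty is about ±1.0 to 2.3 points under the assumed inputs, against about ±0.4 points (post-period) or ±0.6 points (change from baseline) for a reader who treats births as independent. These half-widths are illustrative, since the documents give no caesarean rate, between-facility SD, ICC or CAC. A very large shift would be visible in the table as planned.

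A reader might infer that a caesarean shift would bias the primary result. It would not: any such change is part of the programme's total effect. Its contribution may also be modest. If each added caesarean carried a 2 to 10% excess risk of deep infection (an assumption), a 2-point rise would add 0.04 to 0.20 points to the composite, against a design effect of 0.75 points (3% to 2.25%). The issue is interpretation of the result. The change is worth making because it is specific and cheap.

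**What to change.** In SAP section 26, keep the descriptive table and add an analysis of caesareans over total births using the constrained-baseline model of SAP section 25.2.2.2. Report the risk ratio and risk difference with 95% confidence intervals and no significance test, as for the secondary outcomes.

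Two details need stating. Define the denominator, including whether total births counts stillbirths, because SAP section 25.2.2.2 uses live births and the stillbirth analysis uses live births plus stillbirths. Also say that facilities are analysed as allocated and that this is an exception to SAP section 22.2, which groups facilities for safety by whether they began the programme. Without that sentence the SAP would give two analysis sets for one safety outcome.

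The cost is a short SAP amendment and one extra model on counts already collected. The downside is one more exploratory interval, to be read with the same caution as the other secondary results.
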